3.1 STUDY CENTER(S)

Up to 40 centers in the United States

3.2 STUDY POPULATION

Study population includes treatment-experienced HIV-infected patients with CCR5-tropic virus who demonstrates evidence of HIV-1 replication despite ongoing antiretroviral therapy with documented genotypic or phenotypic resistance to ART drugs within three drug classes (**or** within two drug classes with limited treatment option). The options may be limited as a result of drug antiviral class cross-resistance, documented treatment intolerance, documented objective assessments such as renal or hepatic insufficiency (e.g. high creatinine at baseline, limiting treatment options due to potential for toxicity), past adverse reactions such as hypersensitivity reactions or neuropsychiatric issues that could limit use of currently approved drugs.

3.3 ELIGIBILITY CRITERIA

3.3.1 Inclusion Criteria

Subjects must meet all of the following criteria to be included in the study:

1. Males and females, age ≥ 18 years
2. Exclusive CCR5-tropic virus at Screening Visit as determined by Monogram Biosciences Trofile® Assay
3. Have a history of at least 3 months on current antiretroviral regimen
4. Treatment-experienced HIV-infected patients with documented genotypic or phenotypic resistance to at least one ART drug within three drug classes

OR

Treatment-experienced HIV-infected patients with documented genotypic or phenotypic resistance to at least one ART drug within two drug classes and have limited treatment option. The options may be limited as a result of drug antiviral class cross-resistance, documented treatment intolerance, documented objective assessments such as renal or hepatic insufficiency (e.g. high creatinine at baseline, limiting treatment options due to potential for toxicity), past adverse reactions such as hypersensitivity reactions or neuropsychiatric issues that could limit use of currently approved drugs.

5. Be willing to remain on treatment without any changes or additions to the OBT regimen, except for toxicity management or upon meeting criteria for treatment failure
6. Plasma HIV-1 RNA ≥ 400 copies/mL at Screening Visit as determined by Human Immunodeficiency Virus 1 (HIV-1) Quantitative, RNA (Roche Taqman® Real-Time PCR)

and documented detectable viral load (HIV-1 RNA >50 copies/ml) within the last 3 months prior to Screening Visit

7. Laboratory values at Screening of:
 - a. Absolute neutrophil count (ANC) $\geq 750/\text{mm}^3$
 - b. Hemoglobin (Hb) $\geq 10.5 \text{ gm/dL}$ (male) or $\geq 9.5 \text{ gm/dL}$ (female)
 - c. Platelets $\geq 75,000/\text{mm}^3$
 - d. Serum alanine transaminase (SGPT/ALT) $< 5 \times$ upper limit of normal (ULN)
 - e. Serum aspartate transaminase (SGOT/AST) $< 5 \times$ ULN
 - f. Bilirubin (total) $< 2.5 \times$ ULN unless Gilbert's disease is present or subject is receiving atazanavir in the absence of other evidence of significant liver disease
 - g. Creatinine $\leq 1.5 \times$ ULN
 8. Clinically normal resting 12-lead ECG at Screening Visit or, if abnormal, considered not clinically significant by the Principal Investigator
 9. Both male and female patients and their partners of childbearing potential must agree to use 2 medically accepted methods of contraception (e.g., barrier contraceptives [male condom, female condom, or diaphragm with a spermicidal gel], hormonal contraceptives [implants, injectables, combination oral contraceptives, transdermal patches, or contraceptive rings], and intrauterine devices) during the course of the study (excluding women who are not of childbearing potential and men who have been sterilized). Females of childbearing potential must have a negative serum pregnancy test at Screening visit and negative urine pregnancy test prior to receiving the first dose of study drug
 10. Willing and able to participate in all aspects of the study, including use of SC medication, completion of subjective evaluations, attendance at scheduled clinic visits, and compliance with all protocol requirements as evidenced by providing written informed consent
- Note:** Subjects diagnosed with either substance dependence or substance abuse or any history of a concomitant condition (e.g., medical, psychologic, or psychiatric) may be enrolled if in the opinion of site investigator these circumstances would not interfere with the subject's successful completion of the study requirements

3.3.2 Exclusion Criteria

Subjects meeting any of the following criteria will be excluded from the study:

1. Documented CXCR4-tropic virus or Dual/Mixed tropic (R5X4) virus as determined by HIV-1 tropism assay

2. Patients with no viable treatment options (i.e., no fully active antiretroviral drug available which can be effectively combined to form a viable new OBT)

3. Any active infection or malignancy requiring acute therapy (with the exception of local cutaneous Kaposi's sarcoma)

Note: Subjects infected by the hepatitis B virus or hepatitis C virus will be eligible for the study if they have no signs of hepatic decompensation and meet the liver function tests eligibility criteria

4. Laboratory test values of \geq grade 3 DAIDS laboratory abnormality with the exception of the absolute CD4+ count criterion of $<200/\text{mm}^3$

5. Females who are pregnant, lactating, or breastfeeding, or who plan to become pregnant during the study

6. Unexplained fever or clinically significant illness within 1 week prior to the first study dose

7. Any vaccination within 2 weeks prior to the first study dose

8. Subjects weighing $<35\text{kg}$

9. History of anaphylaxis to oral or parenteral drugs

10. History of Bleeding Disorder or patients on anti-coagulant therapy

11. Participation in an experimental drug trial(s) within 30 days of the Screening Visit

12. Any known allergy or antibodies to the study drug or excipients

13. Treatment with any of the following:

a. Radiation or cytotoxic chemotherapy with 30 days prior to the screening visit

b. Immunosuppressants within 60 days prior to the screening visit

[figure not shown]
c. Immunomodulating agents (e.g., interleukins, interferons), hydroxyurea, or foscarnet within 60 days prior to the screening visit

d. Oral or parenteral corticosteroids within 30 days prior to the Screening Visit.

Subjects on chronic steroid therapy $>5\text{ mg/day}$ will be excluded with the following exception:

○ Subjects on inhaled, nasal, or topical steroids will not be excluded

[figure not shown]
14. Any other clinical condition that, in the Investigator's judgment, would potentially compromise study compliance or the ability to evaluate safety/efficacy

Figure 3-1: Study Flow Diagram

4 STUDY SCHEDULE

As shown in [Figure 4-1](#), this study is divided into three phases: Screening, Treatment and Follow-up.

Figure 4-1: Study Schematic

(1) **Screening Phase:** This phase lasts up to 6 weeks, consists of Screening Visit (SV) and begins with signing of Informed Consent. Assessments performed during this phase determine the subject's final eligibility for study participation. First treatment will be administered within 42 days of Screening Visit.

All subjects will continue taking their existing ART (failed regimen) during the Screening Phase and first week of the Treatment Phase (Part 1).

(2) **Baseline:** The Baseline (T0) visit will take place within 6 weeks of the Screening Visit, as soon as HIV-1 viral tropism, genotypic and/or phenotypic resistance results are available for review by Investigator. HIV RNA and TruCount Assay will be performed to ensure continued eligibility prior to the first Treatment Visit (T1).

(3) **Treatment Phase:** Subjects will receive up to 25 treatments, given approximately every week (window period of ± 3 days) or until treatment failure is experienced, whichever comes first.

The first Treatment Visit (T1) will take place within one week of the T0 visit.

The injectable study treatment (PRO 140) will be administered by a qualified medical

professional (MD, DO, PA, LPN, LVN, NP, RN, or CMA if permitted by state law) or self-administered by subjects.

Note: *Study treatment injections at T1, T2, T3, T7, T11, T15, T19 and T23 must be administered at clinic. The remaining study treatment injections may be self-administered by subjects outside the clinic.*

Any time during Treatment Period Part 2, if treatment failure occurs, Investigator will readjust antiretroviral regimen based on HIV-1 genotypic and/or phenotypic drug resistance results obtained during the TF visit.

Subjects will be allowed to continue PRO 140 with existing OBT regimen while waiting for new regimen to be constructed by the Investigator.

Treatment failure is defined in terms of virologic non-response and virologic rebound in Part 2 of the Treatment Phase of the study:

a) Virologic non-response is defined as two consecutive viral load results of:

- $<0.5 \log_{10}$ copies/mL decrease in HIV-1 RNA at Day 7 of Treatment Period Part 2. *[Assessment Timepoint: T3 visit]*
- $<1 \log_{10}$ copies/mL decrease in HIV-1 RNA at or after Week 4 of Treatment Period Part 2 unless HIV-1 RNA <400 copies/mL. *[Assessment Timepoint: from T6 up to T25 visit]*
- Confirmed plasma HIV-1 RNA levels ≥ 400 copies/mL at Week 25 of the Treatment Period *[Assessment Timepoint: T25 visit]*

b) Virologic rebound is defined as two consecutive viral load results of:

$\geq 1.0 \log_{10}$ copies/mL increase in plasma HIV-1 RNA above nadir level* in Treatment Period Part 2 *[Assessment Timepoint: from T3 up to T25 visit]* or

*Note: This refers to “Nadir” level in the Treatment Phase which starts from T2 visit

- ≥ 400 copies/mL after suppression to <50 copies/mL in Treatment Period Part 2. *[Assessment Timepoint: from T3 up to T25 visit]*

(4) **Follow-Up Phase:** The duration of follow-up depends on whether or not subject has experienced treatment failure during Treatment Period Part 2.

- Subjects who experience treatment failure within Treatment Period Part 2 will be followed up every 4 weeks until viral suppression is achieved (i.e., plasma HIV-1 RNA levels below level of detection) or up to a maximum of 6 months after cessation of therapy if the treating physician does not feel that there is an antiretroviral regimen that will regain full viral suppression.

- Subjects who do not experience treatment failure at the end of Treatment Period Part 2, will be followed up every 2 weeks for total of 4 weeks.

Procedures to be performed during each of these study phases are described below and provided as a Schedule of Assessments in [Table 4-1](#) and [Table 4-2](#).

Table 4-1: Schedule of Assessments – Screening and Treatment Phase

Procedure/Assessments	Screening Visit	Treatment Phase (26 weeks)																In case of Treatment Failure			
		ART only (1 week)	IP + ART (1 week)		IP + OBT (24 weeks)																
Visit	SV	T0	T1		T2	T3	T4-6	T7	T8 - 10		T11	T12-14	T15	T16-18		T19	T20-22	T23	T24-25	EOT	TF
			(Pre-Rx)	(Post-Rx)					1 week ±3 days since last treatment	1 week ±3 days since last treatment				1 week ±3 days since last treatment	1 week ±3 days since last treatment						
Window Period		Within 6 weeks of the Screening visit	Within 1 week ±3 days since T0		1 week ±3 days since last treatment																
Informed Consent ^[1]	X																				
Eligibility Evaluation ^[2]	X																				
Subject Demographics	X																				
Medical History ^[3]	X		X																		
HIV History	X		X																		
Physical Examination	X		X ^[4]		X ^[4]	X ^[4]		X	X												
Neurological Examination ^[5]			X			X		X		X		X		X		X		X		X	X
Vital Signs ^[6]	X			X	X	X		X		X		X		X		X		X		X	X
Body Mass Index	X																			X	X
ECG	X																				
Complete Blood Count ^[7]	X							X				X		X						X	X
Biochemistry ^[8]	X							X				X		X						X	X
Coagulation Indices ^[9]	X							X				X		X						X	X
Serum Pregnancy Test ^[10]	X																				
Urinalysis ^[11]	X							X				X		X						X	X
HBsAg	X																				
Plasma HIV-1 RNA level	X	X	X		X	X		X		X		X		X		X		X		X	X
TruCount T assay ^[12]	X	X	X		X	X		X		X		X		X		X		X		X	X
PK conc. to PRO 140 ^[13]			X					X				X		X					X	X	

Procedure/Assessments	Screening Visit	Treatment Phase (26 weeks)															In case of Treatment Failure		
		ART only (1 week)		IP + ART (1 week)		IP + OBT (24 weeks)													
Visit	SV	T0	T1		T2	T3	T4-6	T7	T8 - 10	T11	T12-14	T15	T16-18	T19	T20-22	T23	T24-25	EOT	TF
			(Pre-Rx)	(Post-Rx)															
Window Period		Within 6 weeks of the Screening visit	Within 1 week ±3 days since T0	1 week ±3 days since last treatment															
Serum conc. of ART Drugs ^[14]			X					X				X						X	X
Urine Pregnancy Test ^[10]			X																
Pre-enrollment Eligibility		X	X																
PRO 140 + Existing ART Regimen			X																
PRO 140 + OBT Administration				X	X	X	X	X	X	X	X	X	X	X	X	X	X		
Injection Site Reaction Assessment ^[15]				X	X	X	X	X	X	X	X	X	X	X	X	X	X	X	
Injection Site Pain Assessment (VAS) ^[16]				X	X	X	X	X	X	X	X	X	X	X	X	X	X	X	
HIV-1 Trofile® Assay ^[17]	X																		X
HIV-1 Drug Resistance Assay ^[18]	X		X		X	X		X		X		X		X		X			X
HIV-1 PhenoSense® Entry Assay ^[19]	X																		X
Anti-idiotypic antibodies to PRO 140			X					X				X						X	X
Blood sample collection for exploratory analysis ^[20]	X																		X
Adverse Events				X	X	X	X	X	X	X	X	X	X	X	X	X	X	X	
Concomitant Medications	X	X	X	X	X	X	X	X	X	X	X	X	X	X	X	X	X	X	

Foot Notes:

- [1] Informed consent must be obtained prior to patient participation in any protocol-related activities that are not part of routine care.
- [2] Initial evaluation of patient eligibility will be performed by Investigator.
- [3] Medical history, past surgeries, disease history, history of substance abuse, social history, blood transfusion history, and current therapies (medications and non-medication).
- [4] Symptom-directed physical examination
- [5] The neurological assessment tool is based on the three question survey used by Simioni et al. (Simioni S, 2010) Additional neurological assessment modalities may be used as per Investigator's discretion.
- [6] Post treatment vital signs will be recorded at T1-3, T7, T11, T15, T19, T23, EOT and TF visits (i.e., blood pressure, heart rate, respiration rate, and temperature)
- [7] Hemoglobin, Hematocrit (HCT), Red Blood Cells (RBC), White Blood Cells (WBC) with total and differential count, Absolute Neutrophil Count (ANC) and platelets.
- [8] Serum Biochemistry
 - Hepatic function indicators: total and direct bilirubin, alkaline phosphatase, aspartate aminotransferase (AST), alanine aminotransferase (ALT), total protein, Lactate dehydrogenase (LDH)
 - Renal function indicators: BUN, creatinine
 - Electrolytes: sodium, potassium, chloride, calcium and bicarbonate
 - Other: glucose (random), cholesterol (total)
- [9] Prothrombin time (PT) and International Normalized Ratio (INR)
- [10] ONLY performed on women of childbearing potential.
- [11] Urine samples will be tested for color, appearance, specific gravity, pH, protein, glucose, occult blood, ketones, leukocyte esterase, nitrite, bilirubin, urobilinogen, and microscopic examination of urine sediment.
- [12] Includes: CD3 %, CD4 %, CD8 %, Absolute Lymphocytes, CD3 cell count, CD4 cell count, and CD8 cell count
- [13] PK samples for PRO 140 will be collected prior to IP administration at the T1, T7, T15, EOT and TF visits.
- [14] Serum conc. of ART Drugs prior to IP administration at the T1, T7, T15, EOT and TF visits.
- [15] Injection Site Reaction Assessment as assessed by Investigator (or designee) at each treatment visit that occurs in the clinic.
- [16] Subject-perceived injection site pain (average pain since last treatment) will be assessed using the Pain Visual Analog Scale (VAS) prior to each study treatment administration that occurs in the clinic.
- [17] Monogram Biosciences Trofile® DNA and RNA
- [18] Monogram Biosciences PhenoSense® GT and Gensosure Archive (and PhenoSense Integrase and GeneSeq Integrase testing, if applicable)
- [19] Monogram Biosciences HIV-1 PhenoSense® Entry assay with AMD3100 (CXCR4 inhibitor drug), Maraviroc and PRO 140 (CCR5 inhibitor drugs).
- [20] Quest Diagnostics HIV-1 Coreceptor Tropism with Reflex to Ultradeep Sequencing and/or HIV-1 Proviral Tropism

Table 4-2: Schedule of Assessments –Follow-Up (FU) Phase

(a) Subjects who do NOT experience treatment failure

Procedure/Assessments	Follow-Up Visit -1	Follow-Up Visit -2
	NTF-FU1	NTF-FU2
Window Period	2 weeks (±3 days) after EOT visit	4 weeks (±3 days) after EOT visit
Physical Examination	X ^[1]	X ^[1]
Vital Signs	X	X
Plasma HIV-1 RNA level	X	X
TruCount T assay	X	X
Adverse Events	X	X
Concomitant Medications	X	X
Anti-idiotypic Antibodies to PRO 140		X

[1] Symptom-directed physical examination

(b) Subjects who experience treatment failure

Procedure/Assessments	Follow-Up Visit -1	Follow-Up Visit -2	Follow-Up Visit -3 ^[1]
	TF-FU1	TF-FU2	TF-FU3
Window Period	4 weeks (±7 days) after TF visit	8 weeks (±7 days) after TF	12 weeks (±7 days) after TF
Physical Examination	X ^[2]	X ^[2]	X ^[2]
Vital Signs	X	X	X
Plasma HIV-1 RNA level	X	X	X
TruCount T assay	X	X	X
Adverse Events	X	X	X
Concomitant Medications	X	X	X
Anti-idiotypic Antibodies to PRO 140	X		

[1] Subject will be followed up till the viral suppression is achieved or up to a maximum of 6 months after experiencing Treatment Failure (TF) if the treating physician does not feel that there is an antiretroviral regimen that will regain full viral suppression.

[2] Symptom-directed physical examination

4.1 SCREENING PHASE

4.1.1 Pre-Screening

Sites are encouraged to pre-screen subjects for study inclusion, evaluating HIV-1 RNA prior to performing a full screening visit.

The subject will sign and date the pre-screening informed consent form (ICF) prior to any study-related pre-screening procedures. A unique identification number (pre-screening number) will be assigned to each subject who has provided written pre-screening informed consent. The pre-screening number will incorporate a three-digit Study Center number (PS201, PS202, PS203....) and a two-digit numeric ID assigned in successive order of consenting to pre-screening procedures after signing the pre-screening ICF at each center, beginning with 001 at each site (e.g. PS201-01 or PS202-01).

Once the pre-screening ICF has been signed, the following procedures and information will be obtained to confirm pre- eligibility including:

- Review of prior medical records for ART history and resistance to ART drugs
- Blood sample collection for HIV-1 RNA and TruCount assay

A pre-screening log will be maintained to capture the following information:

- Pre-screening number
- Patient initials
- Date pre-screened
- Initial eligibility
- Date of re-consent (for the full consent form) or reason for ineligibility

4.1.2 Screening Visits

The subject (or Legally Acceptable Representative (LAR)) will sign and date the informed consent form (ICF) and Health Insurance Portability Accountability Act (HIPAA) authorization (according to site policy and practices) prior to any study-related procedures. A unique identification number (screening number) will be assigned to each subject who has provided written informed consent. The subject screening number will incorporate a three-digit Study Center number (001, 002 or 003....) and a three-digit numeric ID assigned in successive order of entering the study after signing the ICF at each center, beginning with 001 at each site (e.g. 001- 001 or 002-001).

Subject Screening # :

XXX - YYY

XXX=Study Center

YYY=Subject Numeric ID

All study centers will be instructed to maintain the study-specific pre-screening, screening and enrollment logs at their sites. If a subject initially fails to meet inclusion/exclusion criteria and is later reconsidered for participation, the subject will be re-consented and assigned a new screening number at the time of re-screening. Subjects who fail their first screening attempt may be re-screened a maximum of once and may be enrolled if they are found to meet all inclusion and no exclusion criteria when re-screened.

Once the ICF has been signed, screening procedures and information will be obtained to confirm subject eligibility including:

- Detailed medical history (see [section 7.4](#)),
- Detailed history of HIV infection and treatment (see [section 7.5](#)),
- Demographic information (see [section 7.3](#)),
- Prior and current medications review (see [section 7.6](#)),
- Physical examination (see [section 7.7](#)),
- Electrocardiogram (ECG) (see [section 7.8](#)),
- Body Weight & Height measurements (see [section 7.10](#))
- Vital Signs (see [section 7.10](#)),
- Collection of Blood Specimens (see [section 7.11](#)) for
 - Complete Blood Count
 - Biochemistry
 - Coagulation Indices [Prothrombin time (PT) and INR]
 - Hepatitis B surface antigen (HBsAg)
 - Plasma HIV-1 RNA level
 - TruCount T Assay
 - HIV-1 viral tropism (Tprofile® DNA or RNA Assay)
 - HIV-1 Drug Resistance Assay
 - HIV-1 PhenoSense® Entry (*Monogram BioSciences*)
 - Serum pregnancy test, for female subjects of childbearing potential. Childbearing potential is defined as someone who is not surgically sterile or is not more than one year past complete cessation of menstrual cycles.

- Blood sample collection for Exploratory/Confirmatory analysis
- Collection of Urine Specimen for Urinalysis (see [section 7.11.13](#))

All screening information will be fully documented in the subject's medical records (i.e., source documents).

- For consented subjects who do not meet eligibility criteria, a Screen Failure electronic Case Report Form (eCRF) will be completed. The Screen Failure eCRF will contain the following details: the subject identification number, the date of ICF signature, demographic information (see [section 7.3](#)), and the reason for screen failure. No additional information will be required for subjects who fail screening.
- For consented subjects who meet eligibility criteria, all required screening information will be transcribed onto the appropriate page of the eCRF.

Eligible subjects that are not enrolled within 42 days of Screening Visit will have screening lab assessments repeated, with the exception of HIV-1 viral tropism, genotypic and/or phenotypic resistance, to reconfirm eligibility.

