There was no change in CCR5 virus susceptibility to PRO 140 following treatment. All subjects had CCR5-only virus at screening in the first-generation Trofile assay. CCR5-only tropism results were observed in all subjects at all other timepoints, with two exceptions: One of nine (11%) of placebo subjects had dual/mixed virus at baseline and all subsequent timepoints, reflecting a spontaneous and stable switch in co-receptor tropism results. One of 30 (3%, 0.5 mg/kg group) had a dual/mixed tropism result on day 8 and CCR5-only results at all other timepoints, including the end of the day [Jacobson JM, 2008]. Clonal analysis of the dual/mixed virus revealed that it reflected outgrowth of pre-existing undetected virus rather than mutation of an CCR5 virus to a dual/mixed virus following treatment [Marozsan, 2008]. Therefore, no significant development of viral resistance to PRO 140 was observed despite potent and prolonged (2-3 weeks on average) viral suppression, followed by slow washout of the drug. Given that resistance to other classes of HIV-1 drugs can develop within one week of monotherapy [Demeter LM, 2000] [Saag, 1993][Richman, 1994], the findings indicate that PRO 140 presents a high barrier to viral resistance *in vivo*.

Figure 1-3 illustrates the mean serum concentrations of PRO 140 after IV injection. Serum levels increased with increasing dose. The mean Area Under Curve (AUC) from time zero to infinity

(AUC_{∞}) values were 11.1, 74.3 and 278 mg x day/L for the 0.5, 2 and 5 mg/kg groups. The mean serum half-life was 3.5-3.9 days in the two highest dose groups. In addition, PRO 140 significantly masked CCR5 on circulating lymphocytes for 2-4 weeks [Jacobson JM, 2008]. The PK and receptor occupancy data were broadly consistent with the duration of antiviral effects.

Figure 1-3: PRO 140 1302 Study: PRO 140 serum concentrations following a single intravenous injection in HIV- infected individuals.

The figure illustrates the mean serum concentrations over time by treatment group. The error bars depict standard deviations. The mean serum half-lives were 3.9 days and 3.5 days in the 2 mg/kg and 5 mg/kg dose groups, respectively.

[figure not shown]

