1.4.2.7 PRO 140_CD01 Study

PRO 140_CD01 study (open-label, 43 subjects, multi-center) evaluated the efficacy, safety, and tolerability of PRO 140 monotherapy (350 mg subcutaneous injection weekly for up to 12 weeks) for the maintenance of viral suppression following substitution of antiretroviral therapy

in HIV-1 infected patients (with exclusive CCR5-tropic virus). Participants in this study were experienced HIV-infected individuals who were virologically suppressed on combination antiretroviral therapy. Consenting patients were shifted from combination antiretroviral regimen to PRO 140 monotherapy for 12 weeks.

Forty (40) subjects (M/F: 37/3) with median age of 54.5 years (26-72) and median CD4 T-cell count of 604.5 cells/mm³ (365-1240) were enrolled in the CD01 study. Overall, twenty-two out of 40 (55%) enrolled subjects completed 12 weeks of PRO140 monotherapy without experiencing virologic failure. Virologic failure was defined as two consecutive HIV-1 RNA levels of \geq 400 copies/mL separated by at least 3 days. Of the 40 enrolled subjects, 3 subjects were found to have Dual/Mixed (D/M) tropism [1 at baseline and 2 at the time of virologic failure] and 37 subjects were found to have exclusive CCR5-tropic virus. Fifty-nine percent (59%) of CCR5-exclusive subjects compared to zero percent (0%) of D/M subjects experienced virologic success within 12 weeks of PRO140 monotherapy ($p=0.0465$). All virologic failure subjects who had available lab data in both studies achieved viral suppression to < 400 HIV-1 RNA copies/mL, as well as viral suppression to 'Non Detectable' or < 50 HIV-1 RNA copies/mL after re-initiation of ART.

The by-subject analysis of PhenoSense® Entry Assay data for PRO140, maraviroc, and AMD3100 shows no significant changes in the post-treatment IC50 and IC90 values were noted when compared with baseline values in virologic failure and non-virologic failure groups of subjects. As the aggregate analysis shows, the subjects who experienced virologic failure had higher IC90 value for PR0140 at baseline compared to subjects without virologic failure. The mean IC90 for subjects who experienced virologic failure was higher (10.84 μ g/mL) than the IC90 for subjects without virologic failure (6.70 μ g/mL) in the CD01 study ($p=0.0115$).

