7.11.8 HIV-1 Trofile® Assay

- Includes:
 - a. Trofile® RNA Assay
 - b. Trofile® DNA Assay

Trofile® RNA is the primary assay used to assess HIV-1 co-receptor tropism status. However, Trofile® DNA can be used at the discretion of the Investigator when last recorded viral load is less than 1000 copies/mL.

- Frequency of testing: At SV and TF visits

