8.2.3 Safety Assessments

Safety measurements will include:

- Emergence of Dual/Mixed (D/M)- and CXCR4-tropic virus in patients who had exclusive CCR5-tropic virus at study entry

- Tolerability of repeated subcutaneous administration of PRO 140 as assessed by study participants (using Visual Analogue Scale) and by investigator-evaluation of injection site reactions
- Frequency of treatment-related adverse events resulting in study drug discontinuation
- Frequency of Grade 3 or 4 adverse events as defined by the DAIDS Adverse Event scale
- Frequency of treatment-emergent serious adverse events

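### Tropism is sampled only at Screening and at treatment failure, so dual/mixed or CXCR4 virus found at failure cannot be dated before or after the first PRO 140 dose

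*Protocol*

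**What the plan says.** **Eligibility.** Inclusion criterion 2 (Protocol 3.3.1) requires "Exclusive CCR5-tropic virus at Screening Visit as determined by Monogram Biosciences" Trofile.

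**Sampling.** For Trofile, section 7.11.8 gives "Frequency of testing: At SV and TF visits". The PhenoSense Entry assay (7.11.10) and the sequencing-based tropism test (7.11.12) have the same two time points, and Table 4-1 agrees. The T0 visit (4.2) draws HIV-1 RNA and TruCount. The pre-treatment bloods at T1 (4.3.1) add PK, anti-idiotypic antibodies, ART concentrations and a drug resistance sample, but no tropism sample.

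**Timing.** Section 4 states: "First treatment will be administered within 42 days of Screening Visit". Sections 4.3 and 8.1 also give six weeks. However, section 4 and Table 4-1 allow T0 itself up to six weeks after screening, with T1 following. Section 4.1.2 provides for eligible subjects not enrolled within 42 days: their screening labs are repeated, "with the exception of HIV-1 viral tropism, genotypic and/or phenotypic resistance, to reconfirm eligibility".

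**Use of the result.** The first safety assessment in section 8.2.3 is emergence of D/M or CXCR4 virus "in patients who had exclusive CCR5-tropic virus at study entry".

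**The concern.** The screening sample is the only result that can stand for tropism at study entry, and the next one is taken only if the subject fails. A change from CCR5-only to D/M or CXCR4 between those two samples could have happened before or after the first dose, and nothing collected tells the two apart. There is no control arm to show how often such changes occur without PRO 140.

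A D/M result at TF would then be read as treatment-emergent, in data meant to supplement a licence application. A statistical analysis plan cannot repair this, because the sample that would settle the question is never taken. Section 7.2 asks the investigator to reassess eligibility at T1, but no new tropism result exists to reassess.

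The sponsor's own programme shows that the question arises. In study 1302 all subjects were CCR5-only at screening, yet one of the nine "placebo subjects had dual/mixed virus at baseline and all subsequent timepoints, reflecting a spontaneous and stable switch in co-receptor tropism results". That case could be set apart from a drug effect because 1302 had tropism results at baseline and a placebo arm. This trial has neither.

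**Working it through.** The protocol states no figure on this point to reproduce. The sample size rests on clinical judgement, with no error rate or power.

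**1. Tropism samples by visit**

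| Visit | Tropism sample | Source |
|---|---|---|
| Screening | Trofile, PhenoSense Entry, sequencing-based test | 7.11.8, 7.11.10, 7.11.12 |
| T0 | none | 4.2 |
| T1 before dosing | none (resistance sample drawn and stored) | 4.3.1, 7.11.9 |
| T2 to T25, EOT | none | Table 4-1 |
| TF | same three assays | 7.11.8, 7.11.10, 7.11.12 |

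**2. Age of the tropism result at first dose**

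- Stated limit in section 4: 42 days.
- Visit windows: T0 by day 42, then T1 within 1 week ± 3 days (Table 4-1), so 42 + 7 + 3 = day 52 at the latest.
- Section 4.1.2, late enrolees: no stated maximum.

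The late-enrolee exemption widens the gap but does not create it. A subject dosed well inside 42 days also has no tropism result after screening.

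**3. Which subjects can be miscounted**

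Tropism is retested only at TF. A pre-dose switch is therefore counted as emergence only if the subject also fails treatment. In all other subjects it goes undetected.

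**4. Scale, from the earlier studies the protocol describes**

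- Study 1302 (1.4.2.4): 1 documented switch between screening and baseline in 39 subjects. 1/39 = 2.6%; exact (Clopper-Pearson) 95% CI 0.1% to 13.5%.
- CD01 (1.4.2.7): of 40 enrolled, "3 subjects were found to have Dual/Mixed (D/M) tropism [1 at baseline and 2 at the time of virologic failure". So 1/40 = 2.5% were D/M at baseline, but that subject's screening result is not given, and this is not a documented switch after screening.

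**5. Illustration for 25 subjects**

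Assume the 1302 rate applies, a treatment failure probability f of 20% to 50% (the protocol gives none), and failure independent of the switch.

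- Expected pre-dose switches: 25 × 1/39 = 0.64.
- Expected miscounts: 0.64 × 0.20 = 0.13, to 0.64 × 0.50 = 0.32.
- Chance of at least one miscount: 1 − (1 − 0.20/39)^25 = 12%, to 1 − (1 − 0.50/39)^25 = 28%.

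The confidence limits of the 1302 rate make even this range very uncertain. One miscounted subject moves the emergence count from 0/25 to 1/25, that is 4 percentage points.

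**The case against.** **Limits of the point.** Six weeks is the stated limit in several sections, and an unlimited age is inferred from silence in one exception clause. A miscount needs a switch and also failure on PRO 140 plus an optimised background of three or more agents, in a population that excludes subjects with no fully active drug available. Safety analysis is descriptive, data are listed by subject, and the error runs against the drug. All of this stands and keeps the point small. It does not date a single switch.

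**Minority virus.** The 1302 subject who was D/M on day 8 only was traced by clonal analysis to pre-existing undetected virus. A CCR5-only T1 result would not have prevented that label. This stands. The ultradeep sequencing at screening is the relevant safeguard there, but it cannot show a change after the screening sample.

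**Left to the analysis plan.** The exact definition of emergence may properly sit there. The sampling schedule cannot.

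**Two stronger readings a reader might infer.**

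- *A near-even chance of a false signal.* Pooling both studies gives 2/79 and 1 − (77/79)^25 = 47%. That is the chance of any pre-dose D/M subject, not of a miscount. It also treats the CD01 subject as a switch after screening, which the protocol does not show.
- *Distortion of the primary endpoint.* In CD01, 59% of CCR5-exclusive subjects "compared to zero percent (0%) of D/M subjects experienced virologic success". Two of those three D/M subjects were identified at failure, so the contrast is partly circular. The setting was 12 weeks of maintenance monotherapy, not a 0.5 log10 fall at one week. This does not support a claim about Part 1 response.

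**Conclusion.** The point holds as a minor design weakness in one safety assessment. For any subject who reaches TF with D/M or CXCR4 virus, the protocol cannot say whether the change came before or after the first dose. The interval at issue is nominally up to 42 days, about 52 on the T0 and T1 windows, and without a stated limit for late enrolees, whose number is unknown.

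The best available indication of frequency is one documented pre-dose switch in 39 subjects (2.6%, 95% CI 0.1% to 13.5%). It comes from a first-generation assay in subjects off therapy for 12 weeks, so it shows scale and is not a forecast. The chance of an actual miscount is smaller than the chance of a switch; the 12% to 28% illustration depends on the assumed failure probability and on independence. Viral load, CD4 count, the primary analysis and the sample size are not affected.

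**What to change.** 1. **Sections 4.3.1 and 7.11.8, Table 4-1.** At T1 before dosing, store a tropism aliquot with the resistance sample that section 7.11.9 already stores. It should suit either Trofile version, since 7.11.8 allows the DNA assay below 1000 copies/mL. Test it for any subject with D/M or CXCR4 virus at TF. No result is needed before dosing.
2. **Section 8.2.3.** Count emergence only when the T1 sample is CCR5-only, and report subjects who were not CCR5-only at T1 separately. Report the screening ultradeep sequencing alongside, because the T1 assay will not detect minority virus below its limit.
3. **Section 4.1.2.** Set a maximum age for the screening tropism result, for example first dose by day 52, and otherwise re-screen with tropism. State that an expired result counts as a failed screening, so that the single permitted re-screen applies, and bring the 42-day statements in sections 4, 4.3 and 8.1 into line.

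The cost is one extra stored aliquot for each of up to about 25 subjects at an existing draw, a few triggered assays, and an occasional re-screen. There is no new visit, and dosing is not delayed for subjects treated within the cap.
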